⁹ CBC with differential should be done 24 to 48 hours after the IMO-2125 injection, to coincide with the post-injection biopsy (if the biopsy is conducted). Chemistry profile and coagulation tests do not have to be conducted if Screening tests were conducted within 7 days of the Cycle 1 Week 1 Visit.

¹⁰PT, aPTT, INR.

¹¹ Blood pressure, heart rate, respiratory rate, and temperature.

¹² Week 2 ECG pre-dose and at 2 hours post-IMO-2125 administration. Week 11 ECG at 2 hours post-IMO-2125 administration.

¹³ Including assessment of melanoma lesions.

¹⁴ In Phase 2, all tumor biopsies are optional. See Section 13.2 of the protocol and the Laboratory Manual for details on the collection of biopsies and analyses of biomarkers.

¹⁵ Biopsy of the injected tumor should occur within 24 to 48 hours after injection (no more than 48 hours).

¹⁶ In Phase 2, blood biomarker samples will be collected from at least 20 patients treated at the IMO-2125 RP2D after which the Sponsor will determine if additional samples are needed. The blood biomarker samples will be collected on Day 1 before IMO-2125 administration, 4 hours after IMO-2125 administration, and 24 to 48 hours (coinciding with the 24-hour PK sample) after the injection. At Week 2 and Cycle 3 Week 8, collect before ipilimumab or pembrolizumab dosing.

¹⁷ Radiologic assessment and Investigator assessment of response at Week 8, Week 17, and Week 29 may be conducted within a \pm 7-day window.

¹⁸ At least every 3 months until progression, start of next melanoma treatment, withdrawal of consent, death, or Sponsor notification that follow up is no longer required.

¹⁹ In Phase 2, response assessed using irRECIST and RECIST v 1.1. Best response to first subsequent treatment should also be captured. Confirmatory scans for CR, PR, and progressive disease should be performed \geq 4 weeks after the date the response was first documented.

²⁰ To minimize bias in the PRO data, the PRO assessments should be completed before study drug administration and AE assessments.

²¹ For patients assigned to the IMO-2125 + pembrolizumab treatment arm, continued pembrolizumab dosing per the approved product label is permitted at the discretion of the Investigator.

²² PK: blood sampling for analysis of plasma concentrations of IMO-2125 and serum concentrations of ipilimumab, and pembrolizumab (See **Error! Reference source not found.**Table 3 of the protocol for specific collection

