4. DETERMINATION OF SAMPLE SIZE

The primary objective of Phase 2 is to assess the preliminary clinical activity, defined as the investigator assessed RECIST v1.1 ORR, of IMO-2125 in combination with ipilimumab or of IMO-2125 in combination with pembrolizumab in subjects with progression on or following PD-(L)1 therapy for metastatic melanoma. Given that two primary hypotheses are being tested (regarding the ORR of IMO-2125 and ipilimumab and the ORR of IMO-2125 and

pembrolizumab), a Bonferroni correction has been applied to the alpha to control for Type I error for the trial.

Assuming the immune-related ORR for subjects who receive ipilimumab alone is at most 11% (the historical response rate in subjects who are PD-1 inhibitor naïve), and a target immune-related ORR of 35% for subjects who receive the IMO-2125 ipilimumab combination treatment, a sample size of 21 subjects would achieve 77% power to detect a 24% difference in response rates using a one-sided significance level of 2.5%.

The IMO-2125 + ipilimumab treatment arm will use a two-stage design with a targeted Type I error rate of 0.025 to test the null response rate of 0.11 against the alternative of at least 35%. With this method, 10 subjects will be treated and monitored for an RECIST v1.1 response in the first stage. For this arm, if 2 or more subjects have an RECIST v1.1 response in Stage 1, then the treatment arm will continue to Stage 2, in which 11 more subjects will be treated. If at least 6 of the 21 total subjects have an RECIST v1.1 response, then the null hypothesis H_0 will be rejected in favor of the alternative H_a . In this treatment arm, this design has statistical power of 77%, an expected sample size of 13.33, and a probability of stopping at the end of the first stage of 69.7% if the response proportion is ≤ 0.11 .

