The IMO-2125 + pembrolizumab treatment arm will use a two-stage design with a targeted Type I error rate of 0.025 to test the null response rate against the alternative of at least 35%. If at least 1 subject has an RECIST v1.1 response in Stage 1, then the treatment arm will continue to Stage 2 and treat 11 additional subjects. If at least 4 of the 21 total subjects have an RECIST v1.1 response, then the null hypothesis H_0 will be rejected in favor of the alternative H_a . In this treatment arm, this design has statistical power of 96%, an expected sample size of 14.41, and a probability of stopping at the end of the first stage of 60% if the response proportion is ≤ 0.05 .

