8.1.1 Confirmed Response using RECIST v1.1

Table 6 shows how the investigator-assessed Best Overall Confirmed Response is assigned for each subject. The table is based on the Best Overall Response confirmation table in the RECIST v1.1 guidelines (Appendix C).

Table 6: Confirmed Response using RECIST V1.1

Visit-Level Response	Next Visit Level Response	Confirmed Response
CR	CR	CR (if visit-level disease assessments are \geq 28 days apart), otherwise SD
CR	PR	PR (if visit-level disease assessments are \geq 28 days apart); otherwise SD
CR	SD	SD
CR, PR, SD	PD	SD
CR, PR	NE	SD
PR	CR, PR	PR (if visit-level disease assessments are \geq 28 days apart); otherwise, SD
PR	SD	SD
SD	SD, CR, PR, PD, NE	SD
PD	PD	PD
NE	NE	NE
CR, PR, SD	No 2 nd visit	SD
PD	No 2 nd visit	PD
NE	No 2 nd visit	NE

CR = complete response, PR = partial response, SD = stable disease, PD = progressive disease,
NE = not evaluable.

The minimum interval for confirmation of CR and PR is 28 days. Subjects must have at least one post-baseline disease assessment to be assigned SD as the best overall response; otherwise, there is no minimum interval for assignment of SD as the best overall response. Because scans of target and non-target lesions can be done on different dates, time between disease assessments is determined using the following algorithm: (1) calculate the time in days between initial and confirmatory scans for all target and non-target lesions separately (confirmatory assessment date - initial assessment date +1); (2) select the minimum time; and (3) compare to 28 days to determine if the confirmation criterion were met. Date of confirmed best overall response is determined using scan dates as follows: if BOR is CR or PR response date is the latest date of target or non-target lesion scan date or else use the assessment date.

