8.1.3 Confirmed Response using irRC and irRECIST

Table 7 incorporates the response confirmation rules indicated in the irRC and irRECIST guidelines (see Appendix B and Appendix D).

Table 7 Confirmed Response using irRC or irRECIST

Visit-Level Response	Next Visit-Level Response	Confirmed Response
CR	CR	CR (if visit-level disease assessments are \geq 28 days apart), otherwise SD
CR	PR	PR (if visit-level disease assessments are \geq 28 days apart), otherwise SD
CR	SD	SD
CR, PR, SD	PD	SD
CR, PR	NE	SD
PR	CR, PR	PR (if visit-level disease assessments are \geq 28 days apart); otherwise, SD
PR	SD	SD
SD	SD, CR, PR, PD, NE	SD
PD	PD	PD (if visit-level disease assessments are \geq 28 days apart), otherwise, NE .
CR, PR, SD	No 2 nd visit	SD
PD	No 2 nd visit	NE
NE	No 2 nd visit	NE

The minimum interval for confirmation of CR, PR and PD is 28 days. Subjects must have at least one post-baseline disease assessment to be assigned SD as the best overall response; otherwise, there is no minimum interval for assignment of SD as the best overall response. The same algorithm as for RECIST v1.1 criteria will be used to determine time between disease assessments for confirmation of CR, PR, and PD.

In some situations, it may be necessary to check across more than two sequential time points in order to determine whether or not a minimum duration criteria has been met. The same logic as used for the pairs of time points should be applied. For example, note the following examples.

- For the triplet CR NE CR, if the minimum criteria for CR duration is met for the interval between the two CR assessments, then **Confirmed Response = CR**. Otherwise **Confirmed Response = SD**.
- For the triplet CR CR CR, if the minimum criteria for CR duration is met for the interval between the first and third CR assessments, then **Confirmed Response = CR**. Otherwise **Confirmed Response = SD**.
- For the triplet PR NE PR, if the minimum interval criteria for PR is met for the interval between the two PR assessments, then **Confirmed Response = PR**. Otherwise **Confirmed Response = SD**.
- For the triplet PR PR PR, if the minimum interval criteria for PR is met for the interval between the first and third PR assessments, then **Confirmed Response = PR**. Otherwise **Confirmed Response = SD**.

For confirmed progression using irRC and irRECIST.

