9.2 Primary Efficacy Analyses

The primary efficacy endpoint, investigator-assessed ORR using RECIST v1.1, will be analyzed for all subjects in the PPIEE population and the first 21 patients in the PIIEE, as well as the PIIEE population and SIIIEE population combined using a one-sided, one sample exact binomial test with $\alpha = 0.025$ in each test. The proportion of subjects achieving a best confirmed response of CR or PR will be tested against the null rates of 0.11 and 0.05 for ipilimumab and pembrolizumab, respectively (Hodi et al, 2010).

The primary efficacy analyses will test the following hypotheses:

H_0 : The ORR assessed using the RECIST v1.1, for subjects in the IMO 2125 + ipilimumab treatment arm, is no larger than 0.11;

H_1 : The ORR assessed using the RECIST v1.1, for subjects in the IMO 2125 +ipilimumab treatment arm, is at least 0.35.

H_0 : The ORR assessed using the RECIST v1.1, for subjects in the IMO 2125 +pembrolizumab treatment arm, is no larger than 0.05;

H_1 : The ORR assessed using the RECIST v1.1, for subjects in the IMO 2125 +pembrolizumab treatment arm, is at least 0.35.

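### The confirmation-interval formula adds one day, so the effective minimum is 27 elapsed days against a stated 28; a minor but definite inconsistency in the rule behind the primary ORR

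*SAP*

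**What the plan says.** SAP Section 8.1.1 states: "The minimum interval for confirmation of CR and PR is 28 days". Table 6 in the same section gives a confirmed CR or PR only where the two visit-level assessments are at least 28 days apart, and SD otherwise.

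Target and non-target lesions may be scanned on different dates, so the section sets out an algorithm. Step 1 computes the time for target and non-target lesions separately as "confirmatory assessment date - initial assessment date +1". The remaining steps are "2) select the minimum time; and (3) compare to 28 days to determine if the confirmation criterion were met".

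Section 8.1.3 carries the rule over to irRC and irRECIST: "The same algorithm as for RECIST v1.1 criteria will be used to determine time between disease assessments for confirmation of CR, PR, and PD". Table 7 again requires at least 28 days apart.

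The footnotes to the Phase 1 and Phase 2 schedules (Section 3.4) ask for confirmatory scans no sooner than "4 weeks after the date the response was first documented". Appendix D sets the same 4-week minimum after first documentation for irRECIST.

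The rule feeds the primary endpoint. Section 9.2 says: "The proportion of subjects achieving a best confirmed response of CR or PR will be tested against the null rates of 0.11 and 0.05". Section 4 sets the rejection rules: "If at least 6 of the 21 total subjects have an RECIST v1.1 response" for the ipilimumab arm and "If at least 4 of the 21 total subjects have an RECIST v1.1 response" for the pembrolizumab arm.

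**The concern.** A difference between two dates is the elapsed time between them. Adding one counts both end days, which suits a duration that includes its first day but not a minimum gap. Compared with 28, the sum admits a gap of 27 days. The formula and the threshold in the same paragraph therefore disagree by a day.

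The section is a programming instruction. A programmer who follows the formula and one who follows Table 6 would classify the same subject differently, one as a confirmed response and the other as SD. For the RECIST v1.1 ORR the error runs one way: it can add a confirmed responder but cannot remove one. Under irRC and irRECIST, a pair of PD assessments 27 days apart would count as confirmed progression where Table 7 gives NE.

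**Working it through.** **Inputs.** The formula, the take-the-minimum step and the 28-day comparison come from Section 8.1.1. Scan weeks 8, 17 and 29, each with a ±7-day window, come from the Phase 2 schedule footnotes. The cut-offs of 6/21 and 4/21 come from Section 4. The null rates 0.11 and 0.05 and the one-sided alpha of 0.025 come from Section 9.2.

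**Step 1: does the formula reproduce the 28-day minimum?** It does not.

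| Elapsed gap (days) | Formula (gap + 1) | Formula ≥ 28? | Gap itself ≥ 28? |
|---|---|---|---|
| 26 | 27 | no | no |
| 27 | 28 | **yes** | **no** |
| 28 | 29 | yes | yes |
| 29 | 30 | yes | yes |

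The two rules differ at a gap of 27 days and nowhere else.

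**Step 2: does taking the minimum repair it?** No. With a target gap of 27 and a non-target gap of 30, min(27 + 1, 30 + 1) = min(28, 31) = 28, which passes.

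**Step 3: which scans are exposed?** With scans at opposite edges of their windows, the shortest scheduled gaps are:

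- Weeks 8 to 17: (17 − 8) × 7 − 14 = 63 − 14 = 49 days
- Weeks 17 to 29: (29 − 17) × 7 − 14 = 84 − 14 = 70 days

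Both are far above 28. Only an additional confirmatory scan between scheduled visits can fall at 27 days.

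**Step 4: does a later scan rescue the classification?** Often it does. Take a response at nominal Week 8, seen again 27 days later and still present at nominal Week 17. The second and third assessments are 63 − 27 = 36 days apart, or 36 − 7 = 29 days if Week 17 falls at its early edge. That pair confirms the response without the +1. If the Week 8 scan is also at its late edge, the gap is 49 − 27 = 22 days and this pair alone would not confirm. The first-to-third gap would still be 49 days, which the triplet rule in Section 8.1.3 would accept if it is also read as applying to RECIST v1.1.

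**Step 5: the hypothetical worst case at the cut-off.** P(X ≥ k) = Σ C(21, x) p^x (1 − p)^(21 − x), summed over x = k to 21.

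| Arm | Null rate | One below cut-off | At cut-off |
|---|---|---|---|
| Ipilimumab | 0.11 | 5/21: p = 0.0731 | 6/21: p = 0.0223 |
| Pembrolizumab | 0.05 | 3/21: p = 0.0849 | 4/21: p = 0.0189 |

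In both arms the stated cut-off is the smallest count with p ≤ 0.025, so one added responder just below it changes the result.

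**The case against.** The strongest defence is that this is a day-count convention. The SAP adds one for OS and PFS (Section 8.5), durable-response length (Section 9.3.1) and treatment duration (Section 10.1), and Section 8.1.1 states its formula openly. This does not rescue the rule. Tables 6 and 7 speak of assessments being apart, and the footnotes and Appendix D of time after first documentation. Both describe elapsed time. Nor is the convention uniform: the DoR formula in Section 8.5 has no +1.

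The objections on size do stand. A reader might infer that gaps near 28 days are the expected case, so that misclassification would be common. The documents do not support this. The footnotes set 4 weeks as a floor, not a target, and a scan that respects it passes under either formula. The schedules have a general ±2-day assessment window, but nothing ties it to confirmatory scans, and the SAP gives no distribution of their timing. A response still present at a later scan would usually be confirmed anyway, since Section 8.1 takes the best response across all post-baseline visits.

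A reader might also take 0.073 against 0.022 as the effect of the +1. It is not. It is what any single reclassified subject does in a 21-subject exact test at the threshold. Even at the design alternative of 35%, exactly 6 of 21 has a probability of only about 0.16 (simple binomial), before allowing for the unknown chance of an affected subject.

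**Conclusion.** The contradiction is certain and follows from the SAP's own wording: the stated minimum is 28 days and the formula enforces 27. It enters the confirmed ORR on which both primary tests rest and, through Section 8.1.3, the irRC and irRECIST classifications of CR, PR and PD.

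Its reach is small. A wrong ORR classification needs two things together: a shortest gap of exactly 27 days, and no confirmation by a later assessment because the response was lost or no further evaluable scan was made. A changed primary conclusion also needs the arm to sit exactly at its cut-off. The frequency cannot be estimated from the SAP, so the p-values above are a hypothetical worst case and not an expected effect. The severity is minor.

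**What to change.** In Section 8.1.1, delete the +1, so that the confirmatory date minus the initial date must be at least 28 days for the shorter of the target and non-target gaps. Section 8.1.3 takes the algorithm by reference and needs no separate change. A gap of 27 days then fails and a gap of 28 passes, in line with Tables 6 and 7, the schedule footnotes and Appendix D.

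The cost is one SAP edit and the matching line in the response derivation. If a 27-day pair with no later confirmation exists, the ORR would be slightly lower, and a 27-day PD pair under irRC or irRECIST would be NE unless confirmed later. The edit is best made before any borderline case is seen.

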8.1.2 Best Response at an Interim Analysis using RECIST v1.1

Responses of CR and PR may not have had the opportunity to be confirmed at an interim analysis. Therefore, if a subject has an unconfirmed response (i.e., one visit assessment of CR or PR) as the last disease assessment before an interim analysis, the best response in the interim analysis will be reported as an unconfirmed CR (uCR) or unconfirmed PR (uPR).

8.1.3 Confirmed Response using irRC and irRECIST

Table 7 incorporates the response confirmation rules indicated in the irRC and irRECIST guidelines (see Appendix B and Appendix D).

Table 7 Confirmed Response using irRC or irRECIST

Visit-Level Response	Next Visit-Level Response	Confirmed Response
CR	CR	CR (if visit-level disease assessments are \geq 28 days apart), otherwise SD
CR	PR	PR (if visit-level disease assessments are \geq 28 days apart), otherwise SD
CR	SD	SD
CR, PR, SD	PD	SD
CR, PR	NE	SD
PR	CR, PR	PR (if visit-level disease assessments are \geq 28 days apart); otherwise, SD
PR	SD	SD
SD	SD, CR, PR, PD, NE	SD
PD	PD	PD (if visit-level disease assessments are \geq 28 days apart), otherwise, NE .
CR, PR, SD	No 2 nd visit	SD
PD	No 2 nd visit	NE
NE	No 2 nd visit	NE

The minimum interval for confirmation of CR, PR and PD is 28 days. Subjects must have at least one post-baseline disease assessment to be assigned SD as the best overall response; otherwise, there is no minimum interval for assignment of SD as the best overall response. The same algorithm as for RECIST v1.1 criteria will be used to determine time between disease assessments for confirmation of CR, PR, and PD.

In some situations, it may be necessary to check across more than two sequential time points in order to determine whether or not a minimum duration criteria has been met. The same logic as used for the pairs of time points should be applied. For example, note the following examples.

- For the triplet CR NE CR, if the minimum criteria for CR duration is met for the interval between the two CR assessments, then **Confirmed Response = CR**. Otherwise **Confirmed Response = SD**.
- For the triplet CR CR CR, if the minimum criteria for CR duration is met for the interval between the first and third CR assessments, then **Confirmed Response = CR**. Otherwise **Confirmed Response = SD**.
- For the triplet PR NE PR, if the minimum interval criteria for PR is met for the interval between the two PR assessments, then **Confirmed Response = PR**. Otherwise **Confirmed Response = SD**.
- For the triplet PR PR PR, if the minimum interval criteria for PR is met for the interval between the first and third PR assessments, then **Confirmed Response = PR**. Otherwise **Confirmed Response = SD**.

For confirmed progression using irRC and irRECIST.

- For the triplet PD NE PD, if the minimum interval criteria for PD is met for the interval between the two PD assessments, then **Confirmed Response = PD**. Otherwise **Confirmed Response = NE**.
- For the triplet PD PD PD, if the minimum interval criteria for PD is met for the interval between the first and third PD assessments but is not met between the first and second PD assessments or between the second and third PD assessments, then **Confirmed Response = PD**. Otherwise **Confirmed Response = NE**.

8.1.4 Derivation of irRECIST Confirmed Response for Phase 1 Subjects Treated at the RP2D

For both combinations, subjects enrolled in the Phase 1 portion of the trial will also be analyzed with the Phase 2 subjects. Therefore, the irRECIST response at each visit, as well as the overall confirmed best response, will be derived. These derived responses will be summarized as described in Section 8.1.3.

Visit 1-Screening:- Derived baseline tumor burden will be the sum of the longest diameters of the lesions that have “Yes” for Baseline Target Lesion. Derived non-target lesions will be all lesions identified on the Non-Measurable Disease Assessment page.

Subsequent disease assessments:- Derived tumor burden will be the sum of the longest diameters of all Baseline Target Lesions and lesions identified as new lesions by “Yes” for “Is this a new lesion?” in the Measurable Disease Assessment page of the eCRF. Derived nadir

tumor burden will be the smallest tumor burden across all previous disease assessments, including baseline. Derived non-target lesions will be all lesions identified on the Non-Measurable Disease Assessment page.

Derived Visit Measurable Response:- Using the derived baseline tumor burden, the percentage change from baseline will be calculated as:

Derived percentage change from baseline:

$$\left[\frac{(\text{Derived visit tumor burden} - \text{Derived baseline tumor burden})}{\text{Derived baseline tumor burden}} \right] * 100\%$$

Using the derived nadir tumor burdens, the percentage change from nadir will be calculated for subjects with non-zero derived nadir:

Derived percentage change from nadir:

$$\left[\frac{(\text{Derived visit tumor burden} - \text{Derived nadir tumor burden})}{\text{Derived nadir tumor burden}} \right] * 100\%$$

Subjects who have a value of 0 mm for their derived nadir and a derived tumor burden of at least 5 mm will have a missing derived percentage change from nadir and the derived visit measurable response will be PD. Subjects who have a value of 0 mm for their derived nadir and a derived tumor burden between 0 mm and 5 mm will have a missing derived percentage change from nadir and the derived visit measurable response will be SD. Subjects with a derived nadir of 0 and a derived tumor burden of 0 will have a derived visit measurable response of CR.

Table 8: Measureable Lesion Evaluation

Response	Description of response
irCR	
• Complete disappearance of all non-lymph node lesions and no new measurable or non-measurable lesions.• All measurable lymph nodes have diameter <10 mm in short axis.
irPR	
• $\geq 30\%$ decrease in tumor burden from baseline.
irSD	
• Not meeting criteria for irCR, irPR, or irPD.
irPD	
• $\geq 20\%$ increase in tumor burden from nadir and tumor burden ≥ 5 mm.

NE	
Assigned if “Unable to evaluate longest diameter” is marked for at least one target lesion in the CRF page RECIST v1.1 measurable disease.
----	--

Derived Visit Non-Measurable Response: If there are no new non-measurable lesions, the derived visit non-measurable response is the Status of Non-Target Lesions from the Assessment of RECIST Response page of the eCRF.

Lymph nodes will be identified from “Location” in the Measurable Disease Assessment page of the eCRF.

Table 9: Non-measurable Lesion Evaluation

Response	Status of Non-measurable Lesion (eCRF)
irCR	
Absent
Non-irCR/Non-irPD	
Stable
irPD	
Unequivocal Progression
Not Done/Not Eavaluable	
Assigned if the RECIST v1.1 non-target lesions response is Not Done or Not Evaluable.

If there have been new non-measurable lesions identified, the derived visit non-measurable response will be irPD if any are assessed with “Unequivocal Progression”.

The derived irRECIST response will be determined based on the following:

Table 10: Overall irRECIST Response

Target Lesion (Tumor burden)	Non-Target Lesions	New Lesions: Non-Target	Overall (Time point) Response
irCR	irCR	No	irCR
irCR	Non-irCR/non-irPD	No or Non-Unequivocal Progression	irPR
irCR	NE	No or Non-Unequivocal Progression	irPR

Target Lesion (Tumor burden)	Non-Target Lesions	New Lesions: Non-Target	Overall (Time point) Response
irPR	Non-irPD or not all evaluated	No or Non-Unequivocal Progression	irPR
irSD	Non-irPD or not all evaluated	No or Non-Unequivocal Progression	irSD
Not evaluated	Non-PD	No or Non-Unequivocal Progression	NE
irPD	Any	Yes or No	irPD
Any	irPD	Yes or No	irPD
Any	Any	Uequivocal Progression	irPD

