8.1 Best Overall Response

The best overall response is the best response across all disease assessment visits after baseline taking into account requirements for confirmation. For any response criteria, the best overall response for each subject will be determined by examining investigator-assessed visit-level responses and determining the best confirmed response using the assignment rules in Section 8.1.1 or Section 8.1.2, as appropriate (Paules et al, 2010). Only visit-level disease assessments prior to the start of new anti-cancer therapy or response per the appropriate criteria will be considered.

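### The rule that confirms a response across a non-evaluable scan is printed only for irRC/irRECIST, so an isolated PR-NE-PR is SD on the primary RECIST v1.1 endpoint

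*SAP*

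**What the plan says.** Section 9.2 defines the primary endpoint: "The primary efficacy endpoint, investigator-assessed ORR using RECIST v1.1". It counts responders by confirmed response: "The proportion of subjects achieving a best confirmed response of CR or PR will be tested against the null rates of 0.11 and 0.05".

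Section 8.1 has best confirmed response determined "using the assignment rules in Section 8.1.1 or Section 8.1.2, as appropriate". Section 8.1.2 covers only unconfirmed responses at an interim analysis, so Section 8.1.1 governs the final primary test. There, "Table 6 shows how the investigator-assessed Best Overall Confirmed Response is assigned for each subject". Table 6 works on a visit and the next visit. CR or PR followed by NE is SD, and no row has NE first and CR or PR second. Appendix Table 4 in Appendix C, the source of Table 6, is also pairwise.

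The rule for longer sequences is in the section headed "8.1.3 Confirmed Response using irRC and irRECIST". It says that "it may be necessary to check across more than two sequential time points" and gives examples, among them: "For the triplet PR NE PR, if the minimum interval criteria for PR is met for the interval between the two PR assessments", the confirmed response is PR, otherwise SD. CR-NE-CR is handled in the same way. After the four CR/PR examples a new lead-in, "For confirmed progression using irRC and irRECIST", introduces the two PD examples.

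**The concern.** The trial has one rule set for confirming a response on the primary endpoint and a more permissive one for the same task on a secondary endpoint, with no reason given. A programmer who follows 8.1.1 literally assigns SD to two partial responses months apart with an unreadable scan between them. One who takes the CR/PR examples in 8.1.3 as general assigns PR. The primary responder count would then depend on interpretation, in arms where 6 of 21 or 4 of 21 responders decide the result. Part of any gap between RECIST v1.1 and irRECIST ORR could also come from the derivation rule and not from how the two criteria treat lesions.

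**Working it through.** **1. The classification, with the two sections side by side.**

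Take PR at Week 8, NE at Week 17 and PR at Week 29, the scheduled on-treatment scans in SAP Table 5. Counted from Day 1 of Week 1, Week 8 starts on Day 50 and Week 29 on Day 197. By the SAP's day count the two PRs are 197 − 50 + 1 = 148 days apart, well over 28.

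| Sequence | 8.1.1, Table 6 (pairs) | 8.1.3 (look-across rule) |
|---|---|---|
| PR-NE-PR | SD | PR |
| CR-NE-CR | SD | CR |
| PR-NE-PR-PD | SD | PR |
| PR-NE-PR-PR | PR (last pair) | PR |

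Table 7 has the same row as Table 6 for CR or PR followed by NE. In 8.1.3 the text on longer sequences overrides that row; in 8.1.1 nothing does. The last line of the table shows the limit: any other consecutive CR/PR pair at least 28 days apart still confirms the response under Table 6.

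**2. The plan's own operating characteristics (Section 4).**

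Inputs: Stage 1 n = 10 and Stage 2 n = 11 in each arm. Ipilimumab arm: continue with at least 2 responses, reject with at least 6 of 21, null 0.11. Pembrolizumab arm: continue with at least 1, reject with at least 4 of 21, null 0.05. The alternative is 0.35 in both.

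P(reject) = Σ over k ≥ c1 of Bin(k; 10, p) × P(X2 ≥ c − k), with X2 ~ Bin(11, p), c1 the Stage 1 threshold and c the final threshold. Expected N = 10 + 11 × (1 − probability of early stop).

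| | Power at 0.35 | Early stop under null | Expected N under null | Type I error |
|---|---|---|---|---|
| Ipilimumab, SAP | 77% | 69.7% | 13.33 | target 0.025 |
| Ipilimumab, recomputed | 77.3% | 69.7% | 13.33 | 0.0206 |
| Pembrolizumab, SAP | 96% | 60% | 14.41 | target 0.025 |
| Pembrolizumab, recomputed | 95.9% | 59.9% | 14.41 | 0.0180 |

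The stated figures reproduce.

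**3. One subject at the boundary.**

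One-sided exact binomial p = P(X ≥ x | 21, p0), the test in Section 9.2, against 0.025:

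- Ipilimumab arm, p0 = 0.11: 6/21 gives 0.0223 (reject); 5/21 gives 0.0731 (do not reject).
- Pembrolizumab arm, p0 = 0.05: 4/21 gives 0.0189 (reject); 3/21 gives 0.0849 (do not reject).

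**4. Power if some true responders are lost.**

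The SAP gives no rate for this pattern, so the share lost, m, is an assumption. The response rate becomes 0.35 × (1 − m) in the formula of step 2.

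| Share lost | Effective ORR | Ipilimumab power | Pembrolizumab power |
|---|---|---|---|
| 0% | 35.0% | 77.3% | 95.9% |
| 1% | 34.65% | 76.3% | 95.6% |
| 2% | 34.3% | 75.3% | 95.4% |
| 5% | 33.25% | 72.2% | 94.4% |

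Here m is the share of responders who end with no confirming pair. It is smaller than the share with any NE scan between responses.

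**The case against.** The strongest objection concerns scope. The sentence that opens the look-across rule names no criterion, while the later lead-in limits only the PD examples to irRC and irRECIST. If everything above it were already limited, that line would not be needed. The CR/PR examples may therefore have been meant for all criteria. This stands as far as it goes: a reader might infer that the plan deliberately sets a stricter rule for the primary endpoint, and the text does not establish that. But the examples sit under the irRC/irRECIST heading, Section 8.1 does not point there, and the only stated link between the sections carries the day-count method from RECIST v1.1 into 8.1.3. Nothing carries the look-across rule back.

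Second, nothing in the document says that PR-NE-PR is a confirmed response under RECIST v1.1. Appendix Table 4 gives SD or NE for PR then NE, and Appendix D asks for confirmation at a consecutive assessment even for irRECIST. Aligning the two endpoints by removing the bridge from irRECIST would also be coherent. That stands. Extending it is preferred here because the plan already accepts the bridge as a reading of confirmation at 28 days.

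Third, a reader might take every responder with an intervening NE as lost and infer, at 10% or 15%, ipilimumab-arm power of 66% or 60%. The documents do not support this. Scans continue at least every 3 months until progression, with confirmatory scans at least 4 weeks after a first response, so other qualifying pairs can arise.

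Fourth, irRECIST ORR is only summarised descriptively, and no comparison with RECIST v1.1 is planned. This is correct, and it makes the gap between the two rates a minor matter.

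**Conclusion.** The point holds in a limited form. As printed, a subject with PR-NE-PR or CR-NE-CR, the responses at least 28 days apart and no other qualifying consecutive pair, is SD on the primary endpoint and a confirmed responder by irRECIST. Whether this was intended is unclear, and the ambiguity is itself a defect in a primary responder definition.

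The direction is conservative. Losing responders cannot raise type I error above 0.0206 (ipilimumab arm) or 0.0180 (pembrolizumab arm), so an inference that the false-positive risk is inflated would be wrong. The cost is some power and a responder count open to interpretation. Under an assumed loss of 1% to 5% of true responders, the ipilimumab arm loses about 1 to 5 percentage points of power and the pembrolizumab arm about 0.3 to 1.5. The practical weight comes from the small sample: one reclassified subject at the boundary changes the conclusion in either arm.

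**What to change.** Before database lock, so that the definition is not settled once results are known:

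- State in 8.1.1 that the CR/PR rule for more than two time points in 8.1.3 also applies to RECIST v1.1: CR-NE-CR is CR and PR-NE-PR is PR if the two responses are at least 28 days apart, otherwise SD.
- Add the row for NE followed by CR or PR to Table 6.
- Correct the cross-reference in 8.1 so that it includes 8.1.3.
- State how a visit recorded as Not Done (Section 9.3.1) is handled in confirmation. No example in 8.1.3 bridges a missed scan, so it should not be equated with NE by default.

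The cost is SAP wording and the matching derivation code; no new data are needed.
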